### 3. STUDY DESIGN AND SCHEDULE OF EVENTS

This is a randomized, open-label, controlled phase 2 trial designed to evaluate the safety and tolerability and explore the efficacy of CAP-1002 administered by multi-vessel intracoronary infusion in subjects with cardiomyopathy secondary to DMD. Approximately 24, and not more than 30, subjects will be randomized 1:1 to receive CAP-1002 or usual care. Subjects randomized to receive usual care will continue to be cared for and treated on an ongoing basis in whatever manner the investigator deems most appropriate for the subject. The first 6 subjects enrolled (Group 1) will be older than 18 years of age. Enrollment of the remaining subjects (Group 2) will begin at least two weeks after the final infusion occurs in Group 1 to allow a review of Group 1 safety data through 72 hours post infusion. Subjects in Group 2 will be at least 12 years of age.

CCI

Anatomically  
one of the three coronary arteries infused must supply more than 30% of the LV myocardium.

Subjects will undergo protocol assessments through 12 months post infusion or reference date. Reviews by a Data Safety Monitoring Board (DSMB) will be done after Group 1 completes 72 hours of follow-up and throughout the trial per charter but at least semi-annually. The DSMB will review both safety and efficacy data after all subjects complete 6 months of follow-up or withdraw from the study. In addition, there will be one administrative interim efficacy analysis after Month 6 MRI measurements are available for at least 14 subjects. Subjects will be followed annually for 5 years post infusion or reference date. The Schedule of Events is shown in [Appendix A](#). A schematic of the study design is as follows:

## 4. SAMPLE SIZE

The sample size of approximately 12 subjects per treatment group is adequate to assess safety and tolerability and to explore efficacy.

## 5. RANDOMIZATION

Randomization will be done by a dominant biased coin design within each of 5 blocks of 6 subjects each. This design allows decreasing predictability as more subjects become enrolled. For a given block, let  $D_N = n_c - n_u$ , where  $n_c$  = number randomized to CAP-1002 and  $n_u$  = number randomized to usual care, and  $N$  = total randomized to date,  $N=0$  to 5. For block = B, B=1 to 5, let  $p_{N+1}$  = probability the next assignment will be CAP-1002. Then  $p_{N+1}$  varies according to the following rules:

$$p_{N+1} = 0.5 \text{ if } D_N = 0$$

$$p_{N+1} = p_B \text{ if } D_N > 0$$

$$p_{N+1} = 1-p_B \text{ if } D_N < 0$$

The specific values of  $p_B$  (for each block) will be known only to the study statistician until after database lock.

## 6. ANALYSIS POPULATIONS

The following analysis populations are defined for the trial:

**Safety Population:** Subjects randomized to CAP-1002 treatment who received the IP on Day 0, and all subjects in the usual care treatment group who remain on study as of the reference time point. Subjects will be summarized and analyzed per treatment actually received, regardless of their randomization assignment.

Intent to Treat (ITT) Population: All subjects randomized. Subjects will be summarized and analyzed per their randomization assignment, regardless of the treatment (CAP-1002 or usual care) actually received.

Modified ITT (mITT) Population for Efficacy Parameter X: Subjects in the safety population who have at least one post-baseline observation for Parameter X. Subjects will be summarized and analyzed per their randomization assignment, regardless of the treatment actually received.

Per Protocol Population: Subjects with no major protocol violations. The list of subjects with major protocol violations will be compiled prior to database lock.

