#### 7.13.2 Timing

Adverse event assessment and documentation will occur at every study visit from screening throughout the study. On the day of treatment administration, a subject's medical complaint will be considered to be a treatment-emergent adverse event if the event occurs any time after the first exposure of investigational product at the beginning of the catheterization for the infusion of CAP-1002. For subjects receiving usual care, an event is considered treatment-emergent if it occurs on or after 9:00 am (in the subject's time zone) on Day 0.

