### 9.3 Analysis Populations

- **Intent to Treat (ITT) Population**: All subjects randomized. Subjects will be summarized and analyzed per their randomization assignment, regardless of the treatment (CAP-1002 or usual care) actually received.
- **Modified ITT (mITT) Population**: Subjects in the CAP-1002 treatment group who received the IP, and all subjects in the usual care treatment group who remain on study as of 9:00 am (subject's time zone) on Day 0. Subjects will be summarized and analyzed per their randomization assignment, regardless of the treatment (CAP-1002 or usual care) actually received.
- **Per Protocol Population**: Subjects with no major protocol violations. The list of subjects with major protocol violations will be compiled prior to database lock.
- **Safety Population**: Subjects randomized to CAP-1002 treatment who received the IP, and all subjects in the usual care treatment group who remain on study as of 9:00 am (subject's time zone) on Day 0. Subjects will be summarized and analyzed per treatment actually received, regardless of their randomization assignment.

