### 9.5 Safety Analysis

The primary analysis of safety will be performed on the Safety Population as defined above. Additional analyses will be defined in the SAP.

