#### 7.2.1 Tables and Figures

- Tables and figures will present data summaries and/or analyses for the appropriate study population; e.g., summaries of safety parameters will be shown for the safety population only.
- Treatment group order in tables and figures will be usual care, CAP-1002, and “All Subjects.” Note: not all tables and figures will show data summarized for “All Subjects.”
- Tables and figures will present summaries/analyses by study visit window, if applicable.
- Table column headers and figure legends will include subgroup sample sizes.

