## **8. STUDY POPULATION PARAMETERS**

Listings will be done for the ITT population and summaries for the safety population. Some or all summaries may also be done for other analysis populations defined in [Section 6](#). Study population parameters to be listed and summarized are described below.

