### **8.6 IP Administration**

Details of IP administration will be listed. Successful completion of IP administration, reason for non-completion, combination of coronary territories infused, total dosage, and final TIMI flow score per artery infused will be summarized.

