## 9. SAFETY ANALYSIS

Listings, summaries, and analyses of safety parameters will be done for the safety population. Some or all summaries may also be done for other analysis populations defined in [Section 6](#). Safety parameters are described below.

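### The Safety Population leaves out a CAP-1002 subject whose catheterization was started but who received no cells, so no committed safety summary counts him

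*SAP*

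**What the plan says.** SAP Section 6 admits to the CAP-1002 side of the Safety Population "Subjects randomized to CAP-1002 treatment who received the IP on Day 0". Protocol 9.3 has the same condition: "Subjects randomized to CAP-1002 treatment who received the IP, and all subjects in the usual care treatment group who remain on study" at 9:00 am on Day 0.

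The safety outputs follow that population. Protocol 9.5 states: "The primary analysis of safety will be performed on the Safety Population as defined above". SAP 7.2.1 says, by way of example, that "summaries of safety parameters will be shown for the safety population only". SAP Section 9 assigns safety listings, summaries and analyses to it and adds "Some or all summaries may also be done for other analysis populations defined in" Section 6, which is an option and not a commitment.

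The description of the infusion follows the same rule. SAP Section 8 states: "Listings will be done for the ITT population and summaries for the safety population", again with other populations optional. SAP 8.6 then promises a summary of "Successful completion of IP administration, reason for non-completion, combination of coronary territories infused, total dosage" and final TIMI flow.

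The starting point for treatment-emergent events is worded in three ways. SAP 9.2 counts from the IP administration procedure. Protocol 7.13.2 counts from "the first exposure of investigational product at the beginning of the catheterization for the infusion of CAP-1002". Protocol 9.5.2 counts from first product exposure and does not mention catheterization.

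**The concern.** The primary objective is the safety of CAP-1002 given by intracoronary infusion. Protocol 1.7 says that the risk of giving it lies mainly in passing a guidewire down the coronary arteries to position the infusion catheter. Protocol 6.10.2 lists suspected or confirmed coronary dissection among the criteria for stopping the infusion, subject to the investigator's judgement on continuing.

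A serious complication at that step, before any cells are given, can be the reason why none are given. Membership of the Safety Population then depends on the outcome it is meant to measure. Usual care subjects enter simply by being on study at the reference time; CAP-1002 subjects enter only if the procedure got as far as delivering cells. Any resulting bias favours the product, and with about 12 CAP-1002 subjects a single case visibly changes a table.

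**Working it through.** The documents give no figure on this point, so there is none to reproduce. The check is a reading of the definitions, followed by an illustration of size.

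**1. Can the subject enter the Safety Population?** He was randomized to CAP-1002 and received no product, so he fails the CAP-1002 condition. The other half covers only the usual care group, so analysis by treatment actually received does not bring him back. The SAP's mITT population is drawn from the Safety Population, so he is not there either. He is in the ITT population, for which no safety summary is committed.

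**2. Which outputs include him?**
- Not the committed safety summaries (Protocol 9.5; SAP 7.2.1 and 9).
- Not the committed summary of infusion completion (SAP 8 with 8.6), although it is meant to give reasons for non-completion.
- Not the listing of treatment-emergent events, which SAP 7.2.2 restricts to the Safety Population.
- He does appear in the ITT listings of IP administration and of disposition, where SAP 8.8 foresees an attempt date, and in the population counts of SAP 8.1.
- The listings of any SAE and death promised in Protocol 9.5.2 also catch a serious event.

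A subject given any cells is unaffected, including one harmed in the second or third artery after cells in the first.

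**3. Effect of one case.** SAP 9.1 specifies exact 90% intervals for the composite and its components. Suppose 12 infused subjects have no composite event and one further subject has a composite event during catheterization, before any cells.
- As worded: 0/12 = 0%; upper limit 1 − 0.05^(1/12) = 22.1%.
- Counting the started procedure: 1/13 = 7.7%; lower limit 1 − 0.95^(1/13) = 0.4%; upper limit, the 0.95 quantile of Beta(2, 12), = 31.6%.
- If the extra subject has no event: 0/13; upper limit 1 − 0.05^(1/13) = 20.6%.

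**4. Chance of at least one case.** This is 1 − (1 − r·s)^n, where r is a rate from Protocol 1.7 and s is the share of such events that occur before any cells and prevent infusion. The number of attempts n is 12 (the infusion target) or 15 (half of 30 randomized, an assumption and not a bound). The documents do not give s, so s = 1 is a ceiling and the other columns are assumptions. Each cell shows n = 12 to n = 15.

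| Event, r | s = 1 | s = 0.10 | s = 0.25 | s = 0.50 |
|---|---|---|---|---|
| Death (<0.1%) plus ischemia or infarction (0.05%), at most 0.15% | 1.8–2.2% | 0.2% | 0.4–0.6% | 0.9–1.1% |
| Coronary dissection, below 1% | 11.4–14.0% | 1.2–1.5% | 3.0–3.7% | 5.8–7.2% |
| Any angiography complication, 1.4% | 15.6–19.1% | 1.7–2.1% | 4.1–5.1% | 8.1–10.0% |

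The first two rows use upper limits for r, so their entries are upper limits too. No rate is given for cardiovascular hospitalization, which is also part of MACE.

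**The case against.** The strongest case on the other side has four parts.

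**Rarity.** The 0/12 against 1/13 contrast needs a composite event, and an uninfused subject cannot have the TIMI component, which is noted after infusion. That leaves death, infarction or cardiovascular hospitalization; for the first two the chance is about 1% or less at the assumed shares. A dissection or a minor complication would mostly alter adverse-event rows, for which no interval is promised. The 50% share is also generous. Three arteries are infused, the investigator may continue or change the plan, and 0.4 + 0.38 + 0.37 = 1.15 points of the 1.4% overall rate are access-site, arrhythmia and contrast-sensitivity items, which need not prevent infusion. All of this stands. It limits the weight of the point but does not close the gap.

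**Another reading.** Protocol 7.13.2 places first exposure at the start of catheterization, which could keep the subject in. Equally, SAP 9.2 does not say where the IP administration procedure begins, and the procedural steps in Protocol 6.10.1 are redacted. The ambiguity is real. However, 7.13.2 is a rule for timing events, and neither population definition adopts it.

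**Visibility.** SAE reporting, the reporting to the DSMB of events within 24 hours of intervention, CEC review and the ITT listings would all show the case. That is correct, but none of them puts the subject in a numerator or denominator. SAP Section 9 allows wider summaries, but in an open-label trial that choice could be made after the event is known.

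**A received-treatment set is a normal choice.** It is, and it suits the exposure-based outputs. It is less suitable as the only committed set for procedural risk. Counting attempted subjects can also help the product, as 0/13 shows.

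**Conclusion.** The concern holds on the literal wording of both documents and should be fixed before database lock. It is narrow: it applies only to a CAP-1002 subject whose catheterization was started and who received no cells. What is lost is his place in the summaries; the event itself is still reported.

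One such subject with a composite event separates 0/12 (0% to 22.1%) from 1/13 (7.7%; 0.4% to 31.6%), and adverse-event rows change by the same counts. The chance of a case is small and cannot be fixed from the documents, because the share of complications that prevent all infusion is not stated. At assumed shares of 10% to 50% it is 0.2% to 1.1% for death plus ischemia or infarction, below 1.2% to 7.2% for dissection, and 1.7% to 10.0% for any complication. The case for acting is that the rule makes inclusion depend on the safety outcome, in the direction of safety, and that the remedy is cheap.

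**What to change.** Keep the received-product Safety Population for exposure-based outputs (subject-year rates, donor-specific antibodies, laboratory changes), whose anchor date and baseline are tied to infusion, and for building mITT. Then:

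1. Add to SAP 9.1/9.2 one committed peri-procedural table of all CAP-1002 subjects in whom catheterization for infusion was started, beside usual care. Rows: death, infarction, cardiovascular hospitalization, and AEs and SAEs starting in the window. Use one clock for every CAP-1002 subject, infused or not: from the start of the procedure to 72 hours after that start. For usual care, use 72 hours from the reference time point. The existing 72-hour summary stays as it is.
2. Produce the IP-administration summary of SAP 8.6 for all attempted subjects.
3. Reconcile the treatment-emergent starting point in Protocol 7.13.2, Protocol 9.5.2 and SAP 9.2. As context, the Amendment 2 log records that 7.13.2 was moved from vascular access to product exposure, so the sponsor should state which start applies. The new table does not depend on that choice.

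The cost is one table, a sentence each in SAP 8.6 and 9.1/9.2, and wording in Protocol 7.13.2 and 9.5.2. The table counts events, so it needs no baseline. Attempt dates are already listed under SAP 8.8; that the procedure start time is on the case report form is an assumption. There are two downsides. Peri-procedural rates may look slightly less favourable, and the report will carry two peri-procedural summaries with different denominators and clocks, which must be clearly labelled.

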### 3 INVESTIGATIONAL PLAN

#### 3.1 Overall Study Design and Plan

Male subjects with cardiomyopathy secondary to DMD meeting all inclusion and no exclusion criteria will be randomized. All subjects will be at least 12 years of age. They will be randomized in a 1:1 manner to either intracoronary infusion of CAP-1002 in three coronary arteries supplying the three major cardiac territories of the left ventricle of the heart (anterior, lateral, inferior/posterior) or usual care. In the active treatment arm, all three major cardiac territories will be treated (infused) during a single procedure in an open-label fashion.

Approximately 24, and not more than 30, subjects will be randomized into the study, in two sequential enrollment groups. Safety data from Group 1 will undergo a Data Safety Monitoring Board (DSMB) review prior to initiation of enrollment for Group 2.

The first 6-8 randomized subjects will comprise Group 1, and will include a minimum of 3 subjects completing intracoronary infusion with CAP-1002. The DSMB will conduct a review of interim safety data through 72 hours post-Day 0 for at least 3 infused subjects and for at least 6 subjects overall.

Enrollment of Group 2 will begin per DSMB recommendations following their review of the 72 hour safety data from Group 1. Group 2 will include approximately 18 subjects. Screening and randomization will continue until a total of 12 subjects are infused with CAP-1002 or 30 subjects are randomized into the study, whichever comes first.

CCI

A large rectangular area of the page is completely blacked out, indicating redacted content. The text 'CCI' is printed in red at the top left corner of this redacted area.

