### 7.1 Screening Visit

Written informed consent or assent must be obtained from the subject prior to performing any study-related tasks. Afterwards screening period for that subject will begin and the following screening procedures will be performed (not more than 30 days prior to randomization):

- Review of Inclusion / Exclusion Criteria (Section 4.2 and Section 4.3)
- Collection of demographic information
- Review of medical and cardiac history, and concomitant medications
- Measurement of vital signs (body temperature, HR, BP, and RR), weight and height
- 12-lead ECG
- 24-hour ECG via sponsor-provided continuous cardiac rhythm monitoring system
- Cardiac and limited physical examination
- Cardiac MRI
- Venous blood will be collected for the following:
  - Clinical laboratory tests: serum chemistry, hematology, and serology (HbsAg, anti-HCV, anti-HIV 1/2), Cystatin C, Troponin and CK-MB
  - Biomarkers: Osteopontin, ST2, IL-10, and Galectin-3
  - Exploratory biomarkers (if consent/assent provided)
  - Immunoassay: HLA, DSA, and ELISPOT
  - See 6.5 for additional information on clinical laboratory testing.
- A urine sample will be collected for urinalysis
- PUL Scale
- 6MWT (if capable)
- Pediatric QoL Inventory (PedsQL)
- PODCI
- Spirometry
- Adverse Event Assessment
- Submission of historical cardiac MRI

Subjects must continue to meet all of the inclusion and none of the exclusion criteria before proceeding to randomization. Subjects who do not proceed to randomization for any reason during screening will be withdrawn from the study as screen failures and will have no further follow up.

## 7.2 Randomization, Day 0, and Day 1

Subjects that continue to meet eligibility will be randomized (1:1) to either the active treatment arm (CAP-1002) or usual care arm.

For subjects that are randomized to the usual care arm, Day 0 will be defined as seven (7) days after the date of randomization. For subjects that are randomized to the active treatment arm, Day 0 will be defined as the date of the intracoronary infusion of CAP-1002.

**For subjects randomized to CAP-1002 only**, the infusion visit will include tests and assessments as described below and in accordance with the site's standard operating procedures.

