## Appendix 1 Schedule of Events

Procedure / Event	Screening	Infusion (CAP-1002 only) 		Day 1 (Home)	Day 3 (Phone)	Week 2	Week 6	Month 3	Month 6	Month 12	Early Termination 
Study Day	≤30 days prior to randomization	Day 0		Day 1 	Day 3 (+3)	Day 14 (±3)	Day 40 (±7)	Day 90 (±7)	Day 180 (±14)	Day 360 (±30)	As Needed
		PRE	POST								
Informed Consent	X										
Eligibility Assessment	X	X									
Demographics	X										
Medical History	X	X									
Cardiac History	X	X									
Concomitant Medications	X	X	X			X	X	X	X	X	X
Vital Signs	X	X	X			X	X	X	X	X	X
Weight	X								X	X	X
Height 	X						X	X	X	X	X
12-Lead ECG	X	X	X			X	X	X	X	X	X
Limited Physical Examination	X									X	X
Cardiac Physical Examination	X	X	X			X	X	X	X	X	X
Cardiac MRI	X								X	X	X
Continuous cardiac rhythm monitoring	X			X			X		X	X	X
Clinical Laboratory Tests (includes Chemistry, Hematology, Urinalysis)	X	X	X			X	X	X	X	X	X
Serology 	X										
Osteopontin	X					X	X	X	X	X	X
ST2	X					X	X	X	X	X	X
IL-10	X					X	X	X	X	X	X
Galectin-3	X					X	X	X	X	X	X
Exploratory Biomarkers	X					X	X	X	X	X	X

Procedure / Event	Screening	Infusion (CAP-1002 only) 		Day 1 (Home)	Day 3 (Phone)	Week 2	Week 6	Month 3	Month 6	Month 12	Early Termination 
Study Day	≤30 days prior to randomization	Day 0		Day 1 	Day 3 (+3)	Day 14 (±3)	Day 40 (±7)	Day 90 (±7)	Day 180 (±14)	Day 360 (±30)	As Needed
		PRE	POST								
HLA	X										
DSA	X					X	X	X	X	X	X
ELISpot	X						X				
PUL scale	X						X	X	X	X	X
6MWT	X						X	X	X	X	X
Pediatric QL Inventory	X						X	X	X	X	X
PODCI	X						X	X	X	X	X
Spirometry	X						X	X	X	X	X
Coagulation		X									
Serum Troponin & CK-MB	X	X	X			X			X	X	X
Intracoronary Infusion			X								
Adverse Event Assessment	X	X	X		X	X	X	X	X	X	X

 Day 0 is the infusion date for subjects randomized to CAP-1002. All items listed for Infusion visit and assessments on Day 0 are only applicable for subjects randomized to CAP-1002. Subjects randomized to Usual Care do not have a Day 0 visit.

 Early Termination Visit procedures to be completed at time of withdrawal, should subject be withdrawn before Month 12 Visit. A Cardiac MRI will be conducted provided the subject's most recent study-related Cardiac MRI was conducted at least three months (i.e., 12 weeks) prior to the Early Termination Visit.

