# 10. EXPLORATORY EFFICACY ANALYSIS

Listings of efficacy parameters will be done for the ITT population. Summaries and analyses will primarily be done for the mITT population; some or all summaries and/or analyses may also be done for other analysis populations defined in [Section 6](#). In addition, “last observation” analyses will be done for certain parameters for which some subjects’ final assessments were done too late to be included in the Month 12 analysis window.

Unless otherwise noted, for the final analysis changes from baseline will be analyzed using general linear models with baseline values as covariates. Analyses of the effect of treatment group, time (baseline, Month 6, Month 12), and their interaction will be done using mixed effects linear regression, with subject as a random effect, time and treatment group as fixed effects, and baseline as a covariate. Study site may also be included as a random effect if there is evidence of correlation within study sites (per the interclass correlation coefficient from the unconditional model) and/or if doing so appreciably improves the model fit (e.g., per Akaike’s Information Criterion). Residuals will be evaluated for substantial departure from normality and independent and constant variance and appropriate remedies (e.g., data transformations, detecting and assessing the influence of outliers, alternative analytical approaches) will be attempted when necessary. An unstructured covariance will be the default covariance structure but other structures (e.g., compound symmetry) may be used to evaluate sensitivity to the choice of structure or, if necessary, to achieve convergence.

For the analysis of LV LGE rate of change since baseline compared to rate of change from historical MRI to baseline, rate of change  $RC(t_i)$  for time point  $t_i$ ,  $i = 1$  to 3 (baseline, Month 6, Month 12, respectively), will be calculated as

$$RC(t_i) = (X(t_i) - R(t_i)) / D(t_i)$$

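### The main efficacy set requires infusion in the CAP-1002 arm but only continued participation in usual care, and an ITT analysis to check the effect of this is optional.

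*SAP*

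**What the plan says.** SAP 10 sets the efficacy population: "Summaries and analyses will primarily be done for the mITT population". SAP 6 defines the mITT for each parameter as "Subjects in the safety population who have at least one post-baseline observation for Parameter X", so entry depends first on the safety population, which has a different condition in each arm:

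- CAP-1002: "Subjects randomized to CAP-1002 treatment who received the IP on Day 0".
- Usual care: "all subjects in the usual care treatment group who remain on study as of the reference time point". For this arm, Protocol 7.2 fixes the date: "Day 0 will be defined as seven (7) days after the date of randomization".

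Protocol 9.3 has the same infusion condition in its own mITT, and Protocol 9.4 makes that set primary for efficacy. SAP 15 records that the SAP changed the mITT definition, but does not discuss the difference between arms.

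The Day 0 visit, which includes a repeat eligibility assessment, belongs to one arm. Protocol Appendix 1, footnote 1, says: "All items listed for Infusion visit and assessments on Day 0 are only applicable for subjects randomized to CAP-1002". Enrollment under Protocol 3.1 runs "until a total of 12 subjects are infused with CAP-1002 or 30 subjects are randomized into the study", whichever comes first, which leaves room for subjects who are randomized but not infused.

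On ITT, SAP 10 makes efficacy listings certain. For everything else it says that "some or all summaries and/or analyses may also be done for other analysis populations". The efficacy tables in SAP Appendix B name no ITT version.

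**The concern.** Randomization makes the arms comparable as assigned. The mITT then applies a filter to the CAP-1002 arm that the control arm does not face. A CAP-1002 subject who fails the Day 0 re-check, declines the catheterization or is not infused for any other reason leaves the main efficacy set. A comparable usual-care subject is not re-checked and stays in. If the reason for non-infusion is related to outcome, the mITT difference mixes a treatment effect with a selection effect.

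The results will be read as evidence. SAP 7.3 plans two-sided tests at 0.05, SAP 10.1 to 10.3 call for p-values on changes in MRI, PUL, spirometry and QoL, and SAP 13.2.2 provides for public reporting of Month 6 top-line results. With ITT optional, the choice to run it can be made after the mITT result is known.

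**Working it through.** The plan has no power calculation to reproduce. SAP 4 states about 12 per group with no effect size, SD, power or dropout rate.

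**Inputs from the documents:** 1:1 allocation (Protocol 5.3); stop at 12 infused or 30 randomized (Protocol 3.1); two-sided 0.05 (SAP 7.3).

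**Assumptions:** exactly equal arms; no usual-care loss before Day 0; uninfused subjects do worse than infused subjects by d = 0.5 to 1.0 SD; no baseline adjustment. The documents give no value for d, nor its sign. With the opposite sign, the shift reverses.

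**Formulas,** with n randomized to each arm and m infused:

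- fraction dropped f = (n − m)/n
- shift in the CAP-1002 mean = f × d
- SE of the difference = √(1/m + 1/n), in SD units

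Error is the chance that a two-sample t-test rejects when the all-randomized means are equal, taken from the noncentral t distribution with m + n − 2 degrees of freedom.

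| Randomized | Infused | Dropped from CAP-1002 | SE (SD) | Shift (SD), d = 0.5 / 1.0 | Shift/SE | Two-sided error |
|---|---|---|---|---|---|---|
| 24 | 12 | 0 of 12 | 0.408 | 0 / 0 | 0 / 0 | 5.0% / 5.0% |
| 26 | 12 | 1 of 13 (7.7%) | 0.400 | 0.038 / 0.077 | 10% / 19% | 5.1% / 5.4% |
| 30 | 12 | 3 of 15 (20%) | 0.387 | 0.10 / 0.20 | 26% / 52% | 5.7% / 7.9% |
| 30 | 10 | 5 of 15 (33%) | 0.408 | 0.17 / 0.33 | 41% / 82% | 6.8% / 12.3% |

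For the third row: f = 3/15 = 0.20; shift = 0.20 × 0.5 = 0.10 and 0.20 × 1.0 = 0.20; SE = √(1/12 + 1/15) = 0.387; ratios 0.10/0.387 = 26% and 0.20/0.387 = 52%. The upper-tail rejection rate, which favours CAP-1002 under the assumed sign of d, goes from 2.5% to 4.4% and 7.2%.

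**Under ITT,** with all outcomes obtained, the shift is zero by construction. In 200,000 simulated trials of the third row, the two-sided error was 4.7% (d = 0.5) and 4.2% (d = 1.0).

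**The case against.** Several points on the other side stand.

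- **Efficacy is exploratory.** Safety is the primary objective, no efficacy endpoint is primary, no power is claimed, and SAP 10 applies no multiplicity adjustment. This limits the consequence. It does not remove the point, given the planned p-values and the public Month 6 results.
- **ITT is well prepared.** The SAP defines the population (SAP 6), an anchor date (SAP 7.3), a study-day formula (SAP 7.7) and multiple imputation (SAP 10). What is missing is the commitment to run it.
- **Uninfused subjects are not hidden.** Under SAP 8, listings cover the ITT population. SAP 8.1, 8.6 and 8.8 already plan population membership, reasons for non-completion of administration, and disposition. What is not assured is a comparison of mITT exclusions by arm with reasons.

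A reader might go further and infer that uninfused subjects are sicker, so that the mITT favours CAP-1002. The documents do not support this. Candidacy for catheterization is judged before randomization in both arms (inclusion criterion 7, exclusion criterion 2), and later non-infusion could reflect logistics or preference. Nor is it documented that usual care loses almost nobody: open-label controls may leave within 7 days or have no post-baseline value.

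A reader might also take 3 of 15 as the worst case or the expected one. It is neither. The cap of 30 can be reached with fewer than 12 infused, while the target of about 24, with 12 in each arm, implies no exclusions. The shortfall against 12 is also an imperfect count of exclusions. The synopsis counts completed infusions, whereas the safety population requires only that product was received, so a partly infused subject would stay in the mITT.

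Finally, the planned models carry baseline as a covariate, which could absorb part of any difference in severity. The calculation ignores this.

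**Conclusion.** The concern holds in a limited form. The main efficacy set is selected by different post-randomization rules in the two arms, and the analysis that would show whether this matters is optional. The same infusion condition is in the protocol, so this is not a SAP drafting slip alone.

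The number of uninfused subjects and their prognosis decide direction and size, and the documents give neither. The effect is nil if all are infused, small with 1 of 13 uninfused, and about a quarter to a half of a standard error with 3 of 15 under the assumed gap of 0.5 to 1.0 SD before baseline adjustment. For exploratory tests that is modest, but enough to want the all-randomized result beside the mITT.

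**What to change.** 1. In SAP 10, change *may* to *will* for the ITT analysis of the MRI, PUL, spirometry and QoL changes, using the planned model and the multiple imputation already described there. Report it beside the mITT and add it to the table list in SAP Appendix B.
2. State that an uninfused CAP-1002 subject takes the planned infusion day as Day 0 for follow-up visits and analysis. SAP 7.6 already defines Day 0 by planned infusion, while Protocol 7.2 uses the actual infusion date, so the two must be reconciled. The ITT study-day formula in SAP 7.7 needs a Day 0 for every subject.
3. Report exclusions from the mITT by arm with reasons, building on the outputs in SAP 8, 8.1, 8.6 and 8.8.

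This is a cheap improvement. The protocol synopsis already requires one-year follow-up of all randomized subjects, and the mITT stays in place. The costs are extra runs of planned models, some dilution of the effect in the ITT estimate, and more unadjusted exploratory p-values.
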